9.4 Early Termination Procedures

The following early termination procedures will be performed within 5 days of the date of study discontinuation, if a subject is discontinued from the study:

- AE/SAE recording.
- Clinical laboratory parameters (hematology, clinical chemistry, and urine safety analysis).
- Physical examination.
- Lung function (spirometry pre-bronchodilator and spirometry post-bronchodilator). In case the value of the test(s) do not meet the criteria the subject will need to come back within a 7 day window to repeat the test(s).
- Urine pregnancy.
- Vital signs.
- ECG.
- Information on the risk of smoking, smoking cessation advice, and debriefing on THS 2.2.

If the early termination visit occurs on the same day than a planned visit (e.g. the subject wants to withdraw or is discontinued in the middle of V12), all assessments that have been performed during the planned visit should not be conducted again for the ET procedures. In case an early

Confidentiality Statement

Data and information contained in this document are considered to constitute trade secrets and confidential commercial information, and the legal protections provided to such trade secrets and confidential information are hereby claimed under the provisions of applicable law. No part of this document may be publicly disclosed without the written consent of Philip Morris Products S.A.

termination visit is not performed, the subject will still enter into the 28 days Safety Follow-up Period after the discontinuation date.

Confidentiality Statement

Data and information contained in this document are considered to constitute trade secrets and confidential commercial information, and the legal protections provided to such trade secrets and confidential information are hereby claimed under the provisions of applicable law. No part of this document may be publicly disclosed without the written consent of Philip Morris Products S.A.

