### 12.1.6 Handling of Unplanned and Early Termination Assessment

#### Data

Unscheduled assessments will be in general excluded from the analysis and summary statistics. However certain data planned for scheduled assessments are reported within unscheduled visit forms in the eCRF (e.g. repeated/delayed assessments). Given that it is not practical to re-assign them to the pertaining scheduled visits in the eCRF, these data will be accounted for in the analysis and summaries by applying the following re-mapping algorithm to each unscheduled visit:

- If Unscheduled visit date < enrollment date then analysis timepoint = Screening
- If Unscheduled visit date  $\geq$  enrollment date and < randomization date then analysis timepoint = Enrollment
- If Unscheduled visit date  $\geq$  randomization date then:
  1. Determine the unscheduled visit study day using the visit date until midnight.
  2. Determine the reference scheduled visit as the latest previous ( $\leq$ ) scheduled visit recorded and derive the nominal study day from Table 17.
  3. If unscheduled visit study day  $\leq$  nominal study day of the reference scheduled visit + 30 days then unscheduled visit data will be assigned to the analysis timepoint of the reference scheduled visit (see Table 2); otherwise data will be remapped to the analysis time point using the time windows described in Table 17.

For example, someone missing lab assessments at V7 but performed them at study day 123 as recorded in unscheduled form, would have unscheduled lab assessments not mapped to Month 3 (because performed 31 days later than nominal V7 study day) but mapped to Month 4 (because the unscheduled study day is in the [107, 137] time window of Month 4).

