**Table 17: Mapping of Visits After Randomization**

Analysis Time Point	Nominal Study Day (Study Visit and Week number)	Time Window (in Study Days) for Assessments
Day 1	1	= 1
Month 1	29 (V5, Week 4)	[2, 46]
Month 2	64 (V6, Week 9)	[47, 78]
Month 3	92 (V7, Week 13)	[79, 106]
Month 4	120 (V8, Week 17)	[107, 137]
Month 5	155 (V9, Week 22)	[138, 169]
Month 6	183 (V10, Week 26)	[170, 197]
Month 7	211 (V11, Week 30)	[198, 228]
Month 8	246 (V12, Week 35)	[229, 260]
Month 9	274 (V13, Week 39)	[261, 288]
Month 10	302 (V14, Week 43)	[289, 319]
Month 11	337 (V15, Week 48)	[320, 351]
Month 12	365 (V16, Week 52)	≥ 352

Unscheduled assessments will be labelled as unscheduled and presented together with the re-mapped analysis time point in the listings.

Early Termination Assessments will be mapped using the relative study day using the visit date until midnight. Given that Early Termination visits are in general conducted during scheduled visits, the mapping will be performed using time windows as defined in Table 17, apart from early termination visits before randomization (e.g. subjects enrolled and not randomized) which will be assigned to the Enrollment time point. Early termination visit assessments will be labelled as early termination visit and presented together with the re-mapped analysis time point in the listings.

Data from Unscheduled and Early Termination assessments will be combined with data from scheduled visits in the analysis and summary statistics only if there are not scheduled visit

data for the same parameters at that re-mapped analysis time point, and only if the data are scheduled to be collected at that analysis timepoint.

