### 12.7.4.2.4 Laboratory Abnormalities

The shift in toxicity grades from Baseline to worst grade recorded during the 12-month randomized exposure period will be presented in tables for the clinical chemistry, hematology and urinalysis parameters (Tables 15.2.6.18-15.2.6.23). Details related to the toxicity grading of laboratory abnormalities are available in Section 12.7.4.3 “Clinical Laboratory Evaluation”.

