### 12.7.4.3 Clinical Laboratory Evaluation

Hematology, clinical chemistry and urine analysis parameters to be assessed at V1, V3, V7, V10, and V16 are listed in Table 18.

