Listings for the clinical laboratory will be provided by randomization arm. Data will include the following information: normal/high/low, abnormal clinically significant, Principal Investigator's or designee's comments, change from Baseline, and CTCAE grade. Only CTCAE grades greater than zero will be presented.

Shift tables based on the change from Baseline in CTCAE grades to the worst CTCAE grade after Baseline will also be produced by laboratory parameter, randomization arm and product use pattern category.

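### SAP 12.1.6 keeps most early termination and nearly all unscheduled lab, ECG, physical examination and spirometry results out of the safety tables, and conflicts with the worst-grade lab tables

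*SAP*

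**What the plan says.** SAP 12.1.6 stands under General Considerations. For unscheduled visits the default is "Unscheduled assessments will be in general excluded from the analysis and summary statistics". Delayed or repeated assessments are an exception. They go to the latest attended scheduled visit if they fall within 30 days of its nominal study day, and otherwise to the Table 17 window. ET visits are mapped directly by the Table 17 windows.

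The closing sentence then sets two conditions for both kinds of data. They "will be combined with data from scheduled visits in the analysis and summary statistics only if there are not scheduled visit" data for the same parameter at the mapped time point, "and only if the data are scheduled to be collected at that analysis timepoint". No exception is made for safety.

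The safety sections schedule few visits. For labs, SAP 12.7.4.3 has "Hematology, clinical chemistry and urine analysis parameters to be assessed at V1, V3, V7, V10, and V16". Physical examination (12.7.4.4.2) and spirometry (12.7.4.4.4) follow the same visits. ECG (12.7.4.4.5) is at V1, V10 and V16. Protocol 9.4 says "The following early termination procedures will be performed within 5 days of the date of study discontinuation", and its list includes safety labs, physical examination, spirometry, vital signs and ECG.

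Two places define a worst-grade lab table. SAP 12.7.4.2.4: "The shift in toxicity grades from Baseline to worst grade recorded during the 12-month randomized exposure period will be presented in tables". SAP 12.7.4.3: "Shift tables based on the change from Baseline in CTCAE grades to the worst CTCAE grade after Baseline". Neither refers to 12.1.6. SAP 12.7.4.3 also says labs are summarized at Screening, Baseline and V5 to V16, although its first sentence schedules none at V5, V6, V8, V9 or V11 to V15.

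**The concern.** The extension exists to describe longer exposure, and labs, ECG and physical examination are endpoints over the study's duration (SAP 5.2 and 5.4.1). For a subject who stops between V10 and V16, the ET visit normally supplies the only protocol-required lab, ECG, examination or spirometry result from that added exposure. The V7 and V10 values that remain say nothing about it.

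The values lost are not a random sample. Subjects discontinued for an AE undergo the ET procedures (Protocol 8.6), and unscheduled labs include repeats. If the general rule governs, the lab shift tables are not what their definitions promise. A laboratory finding could then appear among a subject's AEs but not in the worst-grade table.

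**Working it through.** **Inputs.** Table 17 nominal days: V7 = 92, V10 = 183, V11 to V15 = 211, 246, 274, 302 and 337, V16 = 365. Table 17 windows: Month 3 [79, 106], Month 6 [170, 197], Months 7 to 11 together [198, 351], Month 12 from 352. Schedules are those of SAP 12.7.4.3 and 12.7.4.4. Extension subjects must have completed V10 (SAP 6.2.1).

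**The plan's own example.** Labs missed at V7 and done on Day 123: 123 − 92 = 31 > 30, and Day 123 lies in [107, 137], so they map to Month 4, as the SAP says. Labs are not scheduled at Month 4, so the second condition then excludes them. The section introduces this mapping as the way such data enter the analysis.

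**ET in the extension, V10 on its nominal day.**
- Days 184–197 (14 days) map to Month 6, already filled by V10: not used.
- Days 198–351 (154 days) map to Months 7–11, where none of the four assessments is scheduled: not used.
- Days 352–364 (13 days) map to Month 12: used.
- Total 14 + 154 + 13 = 181. Used: 13/181 = 7.2%. Not used: 168/181 = 92.8%.

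**ET held at a scheduled visit.** The SAP says this is the usual case. With the ±5-day window, V11 to V15 run from Day 206 (211 − 5) to Day 342 (337 + 5), all inside [198, 351]. An ET at any of these visits is therefore lost for all four assessments. Protocol 9.4's own illustration, V12, is one of them.

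**ET over the whole period, Days 2–364 (363 days).** This assumes that ET in the original study collects the same assessments.
- Labs, physical examination and spirometry, second condition only: 28 + 28 + 13 = 69; 69/363 = 19%.
- ECG, second condition only: 28 + 13 = 41; 41/363 = 11%.
- Labs, physical examination and spirometry with both conditions and V7 and V10 done on their nominal days: Days 79–91, 170–182 and 352–364, 39/363 = 11%.
- Vital signs are scheduled at every visit, so the second condition never removes them.

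**Unscheduled visits, all visits attended on nominal days.**
- Days 92–119 map to Month 3 and Days 183–210 to Month 6: 56/363 = 15% for labs, physical examination and spirometry.
- ECG: 28/363 = 8%.
- Even these count only if the scheduled value is missing.
- No day before V16 maps to Month 12. With V15 attended and V16 missed, an unscheduled lab on Day 360 maps to Month 11, because 360 ≤ 337 + 30 = 367, and is excluded.

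**Exposure period.** SAP 4.1.1 ends it at the discontinuation date, while ET may follow up to 5 days later. Such an ET value could fall outside the 12.7.4.2.4 table even if 12.1.6 did not apply.

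**Illustrative count of subjects.** The documents give no extension dropout rate. Assuming 5–10% of 0.65 × 950 = 617.5 enrolled subjects stop early, evenly over time: 617.5 × 0.05 × 0.928 ≈ 29 to 617.5 × 0.10 × 0.928 ≈ 57 would have no tabulated result after V10 for these assessments.

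**The case against.** A reader might infer that the worst-grade tables leave out the subjects who stopped, or describe mainly completers. The documents do not support that. Extension subjects have completed V10, so their V7 and V10 results normally remain, and the Safety population is not restricted to completers. Only an ET before Day 79 with no other usable lab leaves a subject without a post-baseline value, and that is a dropout from the original study.

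The strongest counter-argument is that a specific definition prevails over a general rule. SAP 12.1.6 never mentions worst-grade derivation, and the two lab sections set no visit restriction. The reference to V5 to V16 may even show that ET and unscheduled labs were meant to be included. This reading is possible, so one cannot say that the plan definitely drops these values from the worst-grade lab tables. But nothing in the SAP settles it, and the only stated rule on ET and unscheduled data excludes them. For by-visit summaries of the four assessments no competing text exists, apart from the V5 to V16 sentence for labs.

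Other points stand in part:
- Of the four assessments, only labs have a worst-grade table. ECG and spirometry have shift tables, and physical examination has counts.
- AEs are the primary safety assessment, and Grade 2 or higher labs must be reported as, or linked to, an AE or concomitant disease (Protocol 8.4.1). A linked value need not create a new AE, however, and Grade 1 values are reported only if judged clinically relevant.
- Delayed assessments that replace a missing scheduled one can be kept within the 30-day rule. An ET on Days 184–197 is set aside only because a V10 value at most two weeks old exists.
- The percentages count calendar days, not subjects.
- No bias between arms is shown, and no primary endpoint estimate is shown to be affected.

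**Conclusion.** The concern holds as a conflict within the SAP. Read as the general rule it is, 12.1.6 removes most ET results and nearly all unscheduled results for labs, ECG, physical examination and spirometry from the summary tables: 168 of 181 possible extension ET days (93%), and every ET held at V11 to V15. That cannot be squared with the two worst-grade definitions or with lab summaries at V5 to V16.

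The loss is of the late value, not of the subject. The 93% assumes V10 on its nominal day and says nothing about how many subjects stop or when. The 29–57 subjects depend entirely on the assumed 5–10% and even timing. Because AEs, vital signs and listings still capture much of the safety signal, this is a should-fix item to settle before database lock.

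**What to change.** - State in SAP 12.1.6 and 12.7.4.3 that the lab tables of shift to worst CTCAE grade use all post-baseline scheduled, unscheduled and ET values, whatever time point they map to, including ET visits up to 5 days after discontinuation. Refer to this from 12.7.4.2.4.
- Include ET results in the ECG and spirometry/COPD shift tables and the physical examination counts, for example as a separate early termination row.
- Reconcile V5 to V16 in 12.7.4.3 with the V7, V10 and V16 lab schedule.
- Leave the mapping rule unchanged for efficacy endpoints.

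The cost is a few sentences and minor programming, since the data are already collected and listed. There are two downsides. Worst-grade counts may look slightly less favourable. In an open-label study unscheduled retests may also be unevenly ascertained between arms, so the tables should carry a footnote saying that such values are included.

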### **12.1.7 Multiple Comparisons / Multiplicity**

This study has no formal pre-specified hypotheses associated with the study objectives. P-values and confidence intervals for all analyses are presented with no adjustment for multiplicity.

## **12.2 Disposition of Subjects**

The number and percent of subjects will be summarized for the following categories: subjects screened, screen failures, enrolled, enrolled but not randomized, randomized, completed V7, completed V10, completed V16, and discontinued (Table 15.2.1.1).

Screen failures will be summarized by reason for screen failure. Unmet inclusion and exclusion criteria will be listed for each screened subjects having any unmet criterion, indicating the applied protocol version (Listing 15.3.1.2).

All subjects who discontinue the study (either main or extension) will be categorized by their primary reason for discontinuation and summarized by randomization arm for the enrolled population (Table 15.2.1.2). Disposition of subjects and reasons for discontinuation will also be summarized separately. Supportive listings will be provided (Listings 15.3.1.1 and 15.3.1.1.1).

The number and percent of subjects with protocol deviations, and the number of protocol deviations, will be summarized by randomization arm for the Randomized population (Listing 15.3.1.10; Table 15.2.1.3.1). Summaries will be broken down by main deviation category (major/minor), sub-categories and evaluability. Subjects will be counted once per deviation category, and can be counted for more than one deviation category.

The number and percent of randomized subjects included in each analysis population will be summarized by randomization arm for all Screened subjects (Table 15.2.1.3.2). For subjects excluded from the analysis populations this will be broken down by reason for exclusion. Subjects will be counted once per exclusion, and can be counted for more than one exclusion.

Supportive listings will be provided, including any additional comments for tests that are not performed to be included on the listings of individual data (Listings 15.3.1.8 and 15.3.2.4).

## **12.3 Demographics and Other Baseline Characteristics**

The demographic variables and other baseline characteristics such as age, sex, race, body weight, height, BMI and waist circumference will be summarized by 6-month and 12-month

product use pattern categories for the FAS-EX, and stratified as described in Section 12.1.1 for the 12-month product use pattern categories. In addition, the analysis will be presented for the FAS-EX for only those subjects who enrolled into the extension study for both 6-month and 12-month product use pattern categories. Analysis will also be presented by randomization arm for the Safety and PP populations (Listing 15.3.1.7; Tables 15.2.1.4.1.\*, 15.2.1.4.2.\*). The summary will be produced also for the FAS-AR if it is different from the Safety population post-randomization. Other baseline characteristics will also be performed as described below.

There will be no inferential analyses of baseline characteristic data performed; however hypothesis testing will be conducted to assess baseline comparability of THS-use and CC-use product use exposure groups at ]V4, V10[ and ]V4, V16[ (for all the covariates in Table 3) for the FAS-EX by means of Analysis of Variance method and chi-square tests for continuous and categorical variables, respectively (Tables 15.2.1.4.3.1 and 15.2.1.4.3.2). These results will be considered for the analysis as described in Section 12.7.1.2 “Smokers’ Health Profile Endpoints Evaluation”.

Baseline comparability will also be conducted between subjects enrolled and not enrolled in the extension study among those who completed V10 (Table 15.2.1.4.4).

Subject responses, individual educational attainment, annual household income and composite classifications will be listed for the SES questionnaire (see Section 7.2.7 “Socio-Economic Status Questionnaire”). The number and percentage of subjects in each of the socio-economic status gradings will also be summarized (Listing 15.3.1.11; Tables 15.2.1.4.1.\*, 15.2.1.4.2.\*).

Subject response to items from the Prochaska questionnaire (see Section 7.2.4 “Prochaska ‘Stage of Change’ Questionnaire: Intention to Quit Smoking”) will be provided in listings and summary tables (Listing 15.3.1.4; Tables 15.2.1.4.1.\*, 15.2.1.4.2.\*).

Smoking history as collected from the smoking history questionnaire (Section 7.2.3 “Smoking History Questions”) will be listed (Listing 15.3.1.3) and summarized, as well as the number and percentage of subjects in the daily CC consumption level at V1 (“10-19 cig/day” vs. “>19 cig/day”) (Tables 15.2.1.4.1.\*, 15.2.1.4.2.\*).

The number and percent of subjects in each category (THS 2.2/ CC/ No preference) of the answer to subjects’ preference question (Section 7.2.6 “Product Preference Question”) will be listed and summarized (Listing 15.3.1.5; Table 15.2.1.4.1.\*, 15.2.1.4.2.\*).

Other Baseline data on covariates (see Section 7.2.9 “Lifestyle Assessment”) will be listed and summarized (Listing 15.3.1.12; Tables 15.2.1.4.1.\*, 15.2.1.4.2.\*).

## 12.4 Medical History and Concomitant Diseases

Medical history is defined as any condition that started and ended prior to V1. A concomitant disease is defined as any condition that is either detected at V1, and/or is still ongoing at V1.

Medical history and concomitant disease will be coded using Medical Dictionary for Regulatory Activities (MedDRA) version 18 or above and listed separately by randomization arm, System Organ Class (SOC) and Preferred Term (PT) within SOC.

Number and percent of subjects with Medical History and Concomitant diseases will be summarized by product use pattern categories (calculated over the entire 12-month ambulatory period), SOC and PT for the Safety population (Listing 15.3.1.9; Tables 15.2.1.5 and 15.2.1.6).

## 12.5 Measurements of Product Adherence

The product use electronic diary will serve as a tool to measure product adherence, as defined in Section 6.3.3 “Adherence to Product Allocation”. The number of products used daily will be listed and described on the FAS-AR, PP, and Safety populations (Listing 15.3.2.1, 15.3.2.1.1, and 15.3.2.1.2; Tables 15.2.2.1.1-15.2.2.1.3), and the number and percentage of adherent subjects will be described on the FAS-EX, Safety, and FAS-AR populations overall and during periods ]V4, V10[ and [V10, V16[ (Tables 15.2.5.1-15.2.5.3).

## 12.6 Other Data

Urine pregnancy results will be provided in Listing 15.3.1.6 and Attempt to quit smoking will be provided in Listing 15.3.1.13.

## 12.7 Planned Statistical Analyses

### 12.7.1 Primary Analyses

#### 12.7.1.1 Hypotheses

No hypotheses are to be tested. The objective of the study is to determine the effect of THS 2.2 compared to CC at week 52 on the components of the “smokers’ health profile” and to provide additional information to the results of the original study (ZRHR-ERS-09-US) for a prolonged exposure period.

### 12.7.1.2 Smokers' Health Profile Endpoints Evaluation

The following endpoints of the “smokers’ health profile” values at Baseline, at V7, at V10, and at V16 will be log-transformed (basee) prior to the analysis: sICAM-1, 11-DTX-B2, 8-epi-PGF2 $\alpha$ , COHb, and Total NNAL. HDL-C, WBC, and FEV1 will be analyzed in the original scale. Concentration of urinary clinical risk endpoints and BoExp will be adjusted for creatinine, as defined in Section 7.1.1 “Clinical Risk Endpoints and Biomarkers of Exposure in Urine”.

Clinical risk endpoints will be analyzed in the FAS-EX population for the subgroup comparing THS-use with CC-use categories, using a MMRM adjusting for sex, Caucasian origin, visit, value of the endpoint at Baseline and its interaction with visit, product use pattern category and its interaction with visit, and other Baseline covariates relevant for each specific clinical risk endpoint. Site will be included as a random effect [20]. Additional Baseline characteristics are defined for each endpoint of the “smokers’ health profile” in Section 4.1.4 “Covariates for Smokers’ Health Profile Analysis” and summarized in Table 3. Model will include terms for the “Defined Covariates” and for the subset of “Evaluated Covariates” selected if found to be significant at 10% level (between THS-use and CC-use) at Baseline for at least one of the 6-month (same as original study) or the 12-month product use categories (Table 15.2.3.1).

Modeling assumptions are evaluated and model fit is assessed by the analysis of residuals (model diagnostics) and by comparing the values predicted versus the observed endpoint values (calibration).

The SAS code for the mixed model to be used is shown below:

```
Proc mixed data=_data_ method=reml maxiter=200;  
Class subject product_use site sex caucasian_origin visit;  
Model endpoint = baseline sex caucasian_origin product_use visit  
                  product_use*visit baseline*visit <covariates> / ddfm=kr;  
Random site;  
Repeated visit / subject=subject type=un r rcorr;  
Lsmeans product_use*visit / slice=visit alpha=0.05 diff cl pdiff;  
Run;
```

The least squares (LS) means and estimate of the difference along with its 95% CI and 2-sided p-value will be presented in tables for HDL-C, WBC, and FEV1 at V7, V10, and V16. For other clinical risk endpoints of the “smokers’ health profile”, results will be presented back transformed in the original scale as a ratio, as well as percent reduction relative to CC-use (i.e. 1 – THS-use:CC-use ratio) at V7, V10, and V16 (Table 15.2.3.1.1). THS-use vs CC-use will also displayed as forest plots at V7, V10, and V16 (Figure 15.1.1.1) for the FAS-EX population. In case of model convergence issues, this will be reported in the study report

and additional covariance structures will be investigated with the following order: heterogeneous compound symmetry (type=csh), heterogeneous toeplitz (type=toeph), heterogeneous autoregressive (1) (type=arh(1)), and variance components (type=vc).

As the smoking cessation effect will be estimated in the SA-SCR-01 study (NCT02432729), the analysis methods for the estimation of the preserved effect will be detailed in a separate analysis plan (cross-study analysis).

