12.1.2 Definitions for Statistical Data Analysis

Baseline:

In general, Baseline value will be the last assessment at or prior to the V3.

Adherence to product allocation:

Adherence to THS 2.2 is defined as at least 70% THS 2.2 use, with no more than 5 CC during each single day of the randomized exposure period of the main study. The same criteria will be adopted for the extended 6-month period. Subjects in the CC arm will be considered adherent to the randomized product. For both the THS 2.2 and CC arm, any subjects reporting to having quit using tobacco-containing products (e.g. THS 2.2 and CC) will be considered not adherent to the study product allocated. Product adherence will be used for the definition of the per-protocol (PP) population (section 12.4.4).

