## 4.1 Definitions for Statistical Analysis

### 4.1.1 Definition of Special Terms

The following special terms are used in this SAP:

Baseline Value	The last assessment prior to randomization and prior to reported THS use during Run-in.
Conventional Cigarette (CC)	The term ‘Conventional Cigarette’ refers to commercially available cigarettes (manufactured and hand-rolled) and excludes cigars, pipes, bidis, and other nicotine-containing products.
End of study (individual)	Date of the last visit of the subject plus 28 days of Safety Follow-up Period. For subjects lost to follow-up the individual end of study is the discontinuation date.
End of study (whole study)	End of Study for whole study is the last subject individual EOS.
Enrollment	Subjects will be enrolled at V3 in the main study, after all applicable inclusion and exclusion criteria have been satisfactorily met, and then will be enrolled at V10 in the extension study, after all applicable inclusion and exclusion criteria have been satisfactorily met.
12-month Randomized exposure period	From the check-out on V4 of the main study until the check-out on V16 or earlier discontinuation date after randomization.
Extended exposure period	From the check-out on V10 until the check-out on V16 or earlier discontinuation date after randomization.

Safety follow-up	In the main study, after the check-out on V10 if the subject does not enroll in the extension study or after discontinuation, a 28-day safety follow-up will be done. In the extension study, after the check-out on V16 or after discontinuation, a 28-day safety follow-up will be done.
Screen failure	Subjects who signed the informed consent form (ICF) at V10 but do not meet the entry criteria.
Tobacco Heating System 2.2 (THS 2.2)	THS 2.2 is comprised of the following components: Tobacco Stick, Holder, Charger, a Cleaning Tool, a main power supply, and a USB cable.

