### **12.7.2.4 Change in biological and functional markers**

#### **12.7.2.4.1 Lung Function and Cardiovascular diseases markers**

Lung function and Cardiovascular data will be collected at V3, V7, V10, and V16.

Lung function data includes spirometry (FEV1, FVC, FEV1/FVC, FEF 25-75, and bronchodilator reversibility in FEV1) and lung volume data (FRC, VC, TLC, IC and RV), and the brand (trade) name and dose of the bronchodilator. Spirometry data will also be collected at V1. At V1, V10, and V16, pre and post-bronchodilator spirometry test will be conducted, while at V3 and V7 only post-bronchodilator test will be performed. Spirometry predicted values will be standardized to the National Health and Nutrition Examination

Survey III predicted set [21], using the formula by Hankinson et al. [22]. Predicted values for Lung function parameters will be derived by a central provider.

Cardiovascular data include the following:

- MPO, Apo A1 and Apo B, Apo B/Apo A1, LDL-C, hs-CRP in serum.
- Fibrinogen, and homocysteine in plasma.
- Platelet count, and HbA1c in whole blood.
- Albumin in urine (expressed as concentration adjusted to creatinine and as quantity excreted in 24h).
- Blood Pressure, weight, waist circumference.

The level of biological and functional markers and their change from Baseline will be listed, and summarized at V7, V10, and V16 (Listings 15.3.3.1-15.3.3.3, 15.3.6.9, and 15.3.6.11; Tables 15.2.4.5.1-15.2.4.5.3, and 15.2.4.7.1-15.2.4.7.3). RV will be summarized descriptively only. FEV1 %pred (post-bronchodilator) will not be analyzed or presented descriptively with the other lung function data since it is already summarized as a primary endpoint. Albumin in urine expressed as quantity excreted in 24h will be listed only.

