#### **12.7.4.4.4 Spirometry**

Spirometry parameters assessed at V1, V3, V7, V10, and V16 (with and without salbutamol assessments at V1, V10, and V16) will be clinically interpreted (categories: normal, abnormal, abnormal clinically significant) and COPD staging will be evaluated [3].

The number and percentage of subjects with normal/abnormal/abnormal clinically significant results will be summarized together with changes in COPD categories by randomization arm (Listing 15.3.3.3; Table 15.2.6.27.1). Clinically significant shift tables by product use pattern category will be presented (Table 15.2.6.27.2).

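### For WBC and FEV1 %pred the primary model leaves out a second pre-exposure value (V1) that is already collected: a missed low-cost improvement, not an error

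*SAP*

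**What the plan says.** The primary model in SAP 12.7.1.2 carries one pre-exposure value of the endpoint. The text describes it as "adjusting for sex, Caucasian origin, visit, value of the endpoint at Baseline and its interaction with visit", and the SAS code begins "Model endpoint = baseline sex caucasian_origin product_use visit", followed by the interaction of that value with visit and a slot for further covariates.

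Baseline is a single assessment. SAP 4.1.1 defines it as "The last assessment prior to randomization and prior to reported THS use during Run-in". Protocol 12.1.2 says "In general, Baseline value will be the last assessment at or prior to the V3". So V3 is the normal source, and V1 can serve only when V3 is missing.

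Two primary endpoints have earlier values:

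- **FEV1:** SAP 12.7.2.4.1 says "At V1, V10, and V16, pre and post-bronchodilator spirometry test will be conducted, while at V3 and V7 only post-bronchodilator test will be performed". Post-bronchodilator FEV1 therefore exists at both V1 and V3. SAP 12.7.4.4.4 gives the same schedule.
- **WBC:** it comes from the hematology panel, and SAP 12.7.4.3 says "Hematology, clinical chemistry and urine analysis parameters to be assessed at V1, V3, V7, V10, and V16 are listed in Table 18".

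SAP 12.1 pools original-study data from V1 to V10 with the extension data. SAP Table 3 lists no V1 endpoint value among the defined or evaluated covariates, and neither document explains why. The PP, FAS-AR and Dual-use analyses reuse the primary covariates.

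**The concern.** WBC and spirometry vary within a subject from visit to visit, so one reading is a noisy measure of that person's usual level. This has two consequences.

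First, variance that a second reading could explain stays in the residual and widens the 95% CI. The evaluation criterion in SAP 5.4.2 is framed in terms of that interval.

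Second, the primary contrast compares THS-use with CC-use by actual use, so randomization does not protect it. Protocol 12.5.4 accepts this by adding unbalanced covariates to deal with residual confounding. If a subject's stable pre-exposure level is related both to product use and to the V16 value, adjusting for one error-prone reading removes only part of the imbalance.

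V1 precedes randomization and THS use, so adjusting for it cannot introduce post-exposure bias.

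**Working it through.** **Inputs from the documents.** SD 6.4 %pred, 475 randomized per arm, 65% enrolled in the extension, 20% lost or with insufficient diary data, 60% of the THS arm in THS-use (SAP 8). V1 to V2 at most 42 days and V2 to V3 at most 5 days (SAP Table 15), so V1 to V3 is at most 47 days.

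**Assumed, because the documents are silent.** r is the correlation of a pre-exposure value with V16, and k is the correlation between V1 and V3.

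**Step 1: the plan's own figure.** CC-use: 475 × 0.65 × 0.80 = 247. THS-use: 247 × 0.60 = 148. Half-width = 1.96 × 6.4 × √(1/148 + 1/247) = 1.30 %pred. From the chi-square distribution of the sample variance, the probability of a half-width of at most 1.5 is above 99.9%. The plan's claim of more than 90% is reproduced.

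**Step 2: precision with two baselines.** If V1 and V3 predict V16 equally well, the residual variance with two values relative to one is

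(1 − 2r²/(1+k)) / (1 − r²).

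The half-widths below treat 6.4 as the residual SD after one baseline. The SAP does not say which SD it is, so they are illustrative.

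| r | k | Variance ratio | CI narrower by | FEV1 half-width |
|---|---|---|---|---|
| 0.5 | 0.5 | 0.889 | 5.7% | 1.23 |
| 0.7 | 0.7 | 0.830 | 8.9% | 1.19 |
| 0.9 | 0.9 | 0.776 | 11.9% | 1.15 |
| 0.6 | 0.75 | 0.920 | 4.1% | 1.25 |
| 0.8 | 0.9 | 0.906 | 4.8% | 1.24 |
| 0.85 | 0.95 | 0.933 | 3.4% | 1.26 |
| 0.6 | 0.9 | 0.970 | 1.5% | 1.28 |
| 0.5 | 0.95 | 0.992 | 0.4% | 1.30 |

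The gain shrinks when V1 and V3 agree much more closely with each other than with V16. It also shrinks when V1 predicts V16 less well than V3 does. With k = 0.8, V3–V16 correlation 0.7 and V1–V16 correlation 0.6, the variance falls by 0.9%. Under first-order decay (V1–V16 correlation equal to k times the V3–V16 correlation, for example 0.9 × 0.8 = 0.72), the ratio is exactly 1 and nothing is gained. The range is therefore about 0% to about 12%.

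**Step 3: residual confounding.** Assume that each reading is a stable level plus independent error, with reliability k. One baseline leaves a fraction (1 − k) of a true imbalance in that level. Two leave (1 − k)/(1 + k). The relative reduction is k/(1 + k).

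| k | Left with one | Left with two | Reduction |
|---|---|---|---|
| 0.6 | 0.40 | 0.25 | 37.5% |
| 0.8 | 0.20 | 0.11 | 44% |
| 0.95 | 0.05 | 0.026 | 48.7% |

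**Step 4: simulation check.** I ran 2,000 trials with 250 per arm, in which about 60% of one arm was kept by selection on the stable level. Bias in endpoint SD units, one versus two baselines, was 0.083 vs 0.053 at reliability 0.6, 0.044 vs 0.024 at 0.8, and 0.025 vs 0.013 at 0.9. The standard-error ratios were 0.93, 0.90 and 0.88. Direction and size agree with the formulas.

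**The case against.** Adjusting for the last pre-exposure value is standard and valid, and no stated precision figure fails without V1. Both points stand. A reader might infer that the primary estimate is invalid or that the CI target is at risk. Step 1 shows otherwise for FEV1, the only endpoint with a precision calculation.

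The size is uncertain. V1 and V3 are weeks apart while V16 is a year after randomization, so a high k with a lower r is plausible, and there the gain is small. This stands. A reader might infer a guaranteed gain of several percent, but the documents give no correlation to support one.

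The confounding argument needs self-selection on WBC or FEV1 level. SAP 16.2 attributes smoking choices to social, cultural, personal and psychological factors, which a second reading does not address. This stands as a condition. Any absolute bias also needs an assumed imbalance: 0.2 SD at k = 0.8 gives 0.2 × 0.20 = 0.04 SD with one baseline and 0.2 × 0.11 = 0.02 SD with two. In FAS-AR, which is analysed as randomized, self-selection into use groups does not arise.

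The change also has costs. SAP 12.1.4 admits only subjects with complete model terms, so a missing V1 would drop a subject unless a rule is stated. Where Baseline is itself the V1 value, the second covariate would duplicate it. Protocol 7.3.5.1 times spirometry against V3, and the documents do not show fasting or timing conditions at V1, which argues against averaging the two visits. SAP 9 values consistency with the original study, and Month 3 and Month 6 estimates could shift. These points shape the fix but do not remove the case for it. Exact consistency is already loosened, because SAP 12.7.1.2 selects covariates on either the 6-month or the 12-month categories.

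**Conclusion.** The point holds as a missed, inexpensive improvement for WBC and FEV1 %pred. The documents show no V1 measurement of the other six primary endpoints.

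- **Precision:** a 95% CI from about 0% to about 12% narrower, depending on correlations that the documents do not give.
- **Confounding (FAS-EX and PP):** a reduction of roughly 37 to 49% of what a single baseline leaves, assuming reliability 0.6 to 0.95 and independent reading error, and only if the stable level is related to product use. Other confounders are untouched.
- **FAS-AR:** precision only.

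The documents do not support reading this as a flaw that invalidates the primary analysis or as a failure to reach ±1.5 %pred.

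**What to change.** In SAP 12.7.1.2, for WBC and FEV1 %pred only:

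1. Add the V1 value and its interaction with visit as a second baseline covariate. Do not use the mean of V1 and V3; separate terms let the model weight V1.
2. State a rule for a missing V1 and for subjects whose Baseline is the V1 value, for example single imputation from baseline data without regard to product-use group, so that no subject is dropped.
3. Keep V3 as Baseline for change-from-baseline tables.
4. Report the single-baseline model as a sensitivity analysis, for consistency with the original study.

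The cost is an SAP amendment, the added model terms, an imputation rule and one extra set of results for two endpoints. No new data are needed. Month 3 and Month 6 estimates for these endpoints may differ slightly from those of the original study.
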